2.4 Safety objective

To assess the safety and tolerability of each dose of dapagliflozin in reference to that of placebo.

2.5 Exploratory objectives

To explore relationships between dapagliflozin plasma exposure measures and efficacy variables such as reduction in HbA1c from baseline. If necessary, Pharmacokinetic (PK) results will be documented in a separate population PK report.

3. STUDY PLAN AND PROCEDURES

This Clinical Study Protocol has been subject to a peer review according to AstraZeneca standard procedures.

3.1 Overall study design and flow chart

[figure not shown]
This is a Phase 2b, multicentre, randomized, 5-arm, parallel-group, double-blind, placebo-controlled study to evaluate the efficacy and safety of dapagliflozin in Japanese T2DM subjects with inadequate glycemic control on diet and exercise alone.

This study consists of an enrolment visit, a 6-week wash-out phase (Period A), a 4-week single-blind, placebo lead-in phase (Period B), a 12-week double-blind, placebo-controlled treatment phase (Period C), and a 4-week follow-up phase (Period D).

Subjects who have inadequate glycemic control ($\text{HbA1c} \geq 7\%$ but $\leq 10\%$) on diet and exercise alone at Visit 5 (1 week before randomization) are eligible to be randomised.

The study design is shown in [Figure 1](#).

Figure 1 Study flow chart

Enrolment visit (Visit 1)

Subjects will provide informed consent if not done before Visit 1, be enrolled and screened for all applicable inclusion and exclusion criteria, and submit laboratory samples.

There will be 4 types of subjects enrolled:

- Strictly treatment naïve subjects at enrolment, defined as never received medical treatment for diabetes (insulin and/or oral anti-hyperglycaemic agents)
- Relatively treatment naïve subjects at enrolment, defined as received medical treatment for diabetes for less than 30 days since diagnosis. In addition, during the 30-day period prior to enrolment did not receive oral anti-hyperglycemic medication for more than 3 consecutive or more than 7 non-consecutive days. Subjects also should not have a history of insulin therapy within 2 weeks of enrolment (with the exception of insulin therapy during a hospitalization for other causes or use in gestational diabetes).
- Subjects treated with anti-diabetic medication prior to enrolment, defined as previously treated with anti-diabetic medication but have not been treated within 6 weeks of enrolment
- Subjects treated with anti-diabetic medication up to enrolment. Only a single oral anti-hyperglycaemic agent or two agents with less than half of the approved maximal dose for each agent are allowed

Wash-out period - Period A (6 weeks; Visit 2 and Visit 3)

Subjects treated with anti-diabetic medication up to enrolment will enter Period A. Strictly treatment naïve subjects at enrolment, Relatively treatment naïve subjects at enrolment, or subjects treated with anti-diabetic medication prior to enrolment will skip this period and enter the Placebo Lead-in period (Period B).

Period A consists of Visit 2 and 3. If HbA1c is $\leq 8\%$ and FPG ≤ 240 mg/dL at the enrolment visit, subjects will start wash-out at the latest from Visit 2 (Week -10). Washout means to stop taking oral anti-hyperglycaemic agent(s). Subjects will receive dietary counselling according to nutritional recommendations for a healthy lifestyle consistent with Japan Society of Diabetes or similar guidelines and a goal of weight maintenance to be followed for the study duration from the investigator(s). Also, subjects will be given a blood glucose meter and be instructed on its use by site personnel. FPG is measured at Visit 2 (Week -10), and Visit 3 (Week -6), and if FPG is > 240 mg/dL at either of these visits, subjects will be withdrawn from the study.

Single-blind, Placebo Lead-in Phase - Period B (4 weeks; Visit 4 and Visit 5)

Period B is a 4-week dietary and placebo lead-in phase.

Subjects treated with anti-diabetic medication up to enrolment will continue to this phase if FPG is ≤ 240 mg/dL during Period A (Visit 2 and 3). FPG is measured at Visit 4 (Week - 4) and Visit 5 (Week - 1), and if FPG is > 240 mg/dl at either of these visits, subjects will be withdrawn from the study. The three other types of subjects will enter Period B if HbA1c is $\geq 7\%$ and $\leq 10\%$ at the enrolment visit.

Subjects will receive dietary counselling according to nutritional recommendations for a healthy lifestyle consistent with Japan Society of Diabetes or similar guidelines and a goal of weight maintenance to be followed for the study duration from the investigator(s). Subjects who skipped Period A will be given a blood glucose meter and be instructed on its use by site personnel.

In Period B, Single-blind placebo will be used to assess subject's compliance with treatment. Subjects must demonstrate good compliance with investigational products ($\geq 80\%$ and $\leq 120\%$) during Period B, and have HbA1c $\geq 7\%$ but $\leq 10\%$ at Visit 5 (1 week before randomisation) to be eligible for entry into Period C. Subjects will be withdrawn from the study if they do not meet these criteria, and must return all unused investigational products. The Investigators will assess adverse event and provide medical therapy that is clinically needed for the subject.

Double-blind, Placebo-controlled, Treatment Phase - Period C (12 weeks; Visit 6-13)

Eligible subjects will participate in a randomized, double-blind, placebo-controlled treatment phase (Period C). Subjects will be randomized to one of five treatment arms that include dapagliflozin 1 mg, 2.5 mg, 5 mg, 10 mg or placebo in a 1:1:1:1:1 ratio. Subjects will be followed for a total of 12 weeks on double-blind study medication, returning for a visit one week after start of treatment, and then approximately every 2 weeks for evaluation of safety and efficacy. Once a patient is randomised, all visits should be scheduled relative to Visit 6. Any slippage in time from one visit must not accumulate to affect other visits. Period C must be at least 81 days and at the most 87 days (12 weeks \pm 3 days). Subject should not take investigational products prior to study visit at Visit 7, 10 and 12 (Week 1, 6 and 10). Investigational products should be taken soon after completing the study visit examinations.

All randomised Subjects who do not complete Period C will complete Visit 13 (Week 12) study procedures as soon as possible but at the latest within 7 days after discontinuation of investigational products.

Visit 6 (Week 0):

On the day of randomization, subjects will present in the morning after a 10-hour overnight fast including 12 hours abstinence from tobacco and caffeine and 24 hours abstinence from alcohol. Contact the registration centre to randomise eligible subjects. Fasting blood sample (for HbA1c, FPG, fasting insulin, C-peptide, fasting serum lipids, standard safety laboratory panel, markers of bone metabolism and cystatine C), and urine sample (for standard safety laboratory panel and spot urine and 24 hour urine for subjects who give consent) will be obtained. OGTT is performed in only those subjects whose FPG is less than 180 mg/dL at Visit 5 (Week -1). Blood samples for assays of glucose, insulin, and C peptide stipulated in

the protocol will be collected at baseline and throughout the duration of the OGTT, and all urine voided during OGTT will be collected. Subjects will receive their first dose of double-blind investigational products as soon as possible after completion of OGTT.

From Visit 7 (Week 1) to Visit 12 (Week 10):

Fasting blood samples and urine samples will be obtained at every visit. The investigators will assess adverse events, review concomitant medications and review subjects' dietary and exercise compliance. Compliance with investigational products will be assessed at every visit. Pill count will also be done at visits when new investigational products is dispensed and the old bottle returned.

Glucose control will be assessed and compared to the protocol-specific parameters for early termination (See Section 5.8) and subjects who meet the pre-specified hyperglycemia criteria will be discontinued from double-blind study medication and complete all Visit 13 (Week 12) study procedures (See Section 5.8).

Visit 13 (Week 12):

Fasting blood sample (for HbA1c, FPG, fasting insulin, C-peptide, fasting serum lipids, standard safety laboratory panel, markers of bone metabolism, and cystatine C), and urine sample (for standard safety laboratory panel and spot urine, and 24 hour urine for subjects who give consent) will be obtained. At Visit 13(Week 12), 24 hour urine is not performed in subjects who did not complete Period C. OGTT will be performed except for subjects who did not perform OGTT at Week 0, discontinued or whose FPG \geq 180 mg/dl at Visit 12 (Week 10). PK samples are obtained at 60, 90, 120, 180 and 240 minutes after administration of investigational products. If OGTT is performed, the PK samples are obtained simultaneously with OGTT blood samples.

The investigators will assess adverse events, review concomitant medications, review subjects' dietary and exercise compliance, assess compliance with investigational products and collect all the investigational products.

Follow-up Phase – Period D (4 weeks; Visit 14)

All subjects completing period C or those who discontinue study medication during period C will be followed for an additional 4 weeks to assess safety parameters. Between weeks 12 and 16, the Investigator may add, at their discretion, any therapy that is clinically indicated to control the subject's hyperglycemia.

Table 1 Study Plan

Procedure	Screening	Wash-out Period (Period A) ^b		Placebo Lead-in Period (Period B)		Double-blind, Placebo-controlled, Treatment Period (Period C) ^c							Follow-up period (Period D)	
	Wk-12 ~ -10 ^a	Wk -10	Wk -6	Wk -4 Entry lead-in	Wk-1	Wk 0 Randomisation	Wk 1	Wk 2	Wk 4	Wk 6	Wk 8	Wk 10	Wk 12 End of Treatment	Wk 16
Visit	1	2	3	4 (-4w)	5 (-1w)	6	7	8	9	10	11	12	13	14
Informed Consent ^a	X													
Review In/Ex Criteria or Randomization Criteria	X					X								
Complete Medical History	X													
Complete Physical Examination	X			X		X							X	
Brief Physical Examination							X	X	X	X	X	X		X
Vital Signs, Body Weight	X			X		X	X	X	X	X	X	X	X	X
Orthostatic Blood Pressure, Heart rate						X		X	X				X	X
Height, Body Mass Index	X													
Waist Circumference	X					X							X	
ECG				X		X							X	
Concomitant medications	X	X	X	X	X	X	X	X	X	X	X	X	X	X
Dietary/exercise instruction/review		X	X	X	X	X	X	X	X	X	X	X	X	X
Contact Registration Centre	X ^e					X ^e							X ^e	
Dispense Glucose Meter and supplies/provide instructions ^d	X	X	X	X	X	X	X	X	X	X	X	X	X	
Adverse Events Assessment				X	X	X	X	X	X	X	X	X	X	X
Pregnancy Test (urine) (WOCBP only)	X			X		X	X			X			X	

Table 1 Study Plan

Procedure	Screening	Wash-out Period (Period A) ^b		Placebo Lead-in Period (Period B)		Double-blind, Placebo-controlled, Treatment Period (Period C) ^c							Follow-up period (Period D)	
	Wk-12 ~ -10 ^a	Wk -10	Wk -6	Wk -4 Entry lead-in	Wk-1	Wk 0 Randomisation	Wk 1	Wk 2	Wk 4	Wk 6	Wk 8	Wk 10	Wk 12 End of Treatment	Wk 16
Visit	1	2	3	4 (-4w)	5 (-1w)	6	7	8	9	10	11	12	13	14
Standard Safety Laboratory Panel (Blood and urine)	X			X		X	X	X	X	X	X	X	X	X
HbA1c	X ^f				X ^f	X			X	X	X	X	X	X
FPG	X ^g	X ^g	X ^g	X ^g	X ^g	X	X	X	X	X	X	X	X	X
Fasting Insulin, C-peptide	X					X				X			X	
Oral Glucose Tolerance test (OGTT) with 75 g oral glucose solution						X ^h							X ^h	
Postprandial glucose, insulin and C-peptide (during OGTT)						X ^h							X ^h	
Collect urine for glucose, creatinine and sodium concentration (during OGTT)						X ^h							X ^h	
PK Sample collection							X ⁱ			X ⁱ		X ⁱ	X ⁱ	
Spot urine collection	X					X				X			X	X
24hr urine collection ^j						X							X	
Obtain serum sample for markers of bone metabolism						X					X		X	X
Assess glycemic targets (FPG)									X	X	X	X		
Fasting serum lipids: Total-C, LDL-C, HDL-C, TG, and FFA						X							X	
Hepatitis Screen Panel ^k , TSH, and PT/APTT	X													

Table 1 Study Plan

Procedure	Screening	Wash-out Period (Period A) ^b		Placebo Lead-in Period (Period B)		Double-blind, Placebo-controlled, Treatment Period (Period C) ^c							Follow-up period (Period D)	
	Wk-12 ~-10 ^a	Wk -10	Wk -6	Wk -4 Entry lead-in	Wk-1	Wk 0 Randomisation	Wk 1	Wk 2	Wk 4	Wk 6	Wk 8	Wk 10	Wk 12 End of Treatment	Wk 16
Visit	1	2	3	4 (-4w)	5 (-1w)	6	7	8	9	10	11	12	13	14
Cystatine C						X							X	X
Dispense Investigational products				X		X		X			X			
Review Medication Compliance						X	X	X	X	X	X	X	X	

- a Screening procedures may be completed over multiple visit dates. IC should be obtained within 14 days before any study specific procedures performed.
- b Wash-out period is only applicable to subjects treated with anti-diabetic medication up to enrolment, and strictly treatment naïve subjects at enrolment, Relatively treatment naïve subjects at enrolment, or subjects treated with anti-diabetic medication prior to enrolment could skip this period (Visit 2 and 3).
- c All randomized subjects not completing the treatment period should have Visit 13 procedures done as soon as possible but at the latest within 7 days after discontinuation of investigational products, and subsequently enter the 4-week follow-up period.
- d Glucose meter is provided to subjects and they check their blood glucose values if they have symptoms of hypoglycemia.
- e Call Registration Center to enroll subjects when informed consent is obtained at Visit 1, to randomize subjects at Visit 6, and when subject completes Period C or early discontinue Period C.
- f Subjects treated with anti-diabetic medication up to enrolment should have HbA1c ≤ 8% at Visit 1 to enter Period A, and the other type of subjects will enter Period B if HbA1c ≥ 7% but ≤ 10% at visit 1. All subjects should have HbA1c ≥ 7% but ≤ 10% at visit 5 to be randomized.
- g Subjects treated with anti-diabetic medication up to enrolment will be withdrawn if FPG > 240 mg/dL.
- h At Visit 6, OGTT is performed if FPG is <180 mg/dL at visit 5. At Visit 13, OGTT is not performed in subjects who did not perform OGTT at Visit 6, subjects who did not complete period C or subjects whose FPG is ≥ 180 mg/dL at Visit 12. At Visit 13, blood samples are drawn 60, 90, 120, 180 and 240 minutes after administration of 75 g oral glucose solution.
- i Plasma samples for analysis of dapagliflozin are obtained before administration of dapagliflozin at Visit 7, 10 and 12. At Visit 13 plasma samples are obtained at 60, 90, 120, 180 and 240 minutes after administration of dapagliflozin. If the subjects perform OGTT at Visit 13, plasma samples are obtained simultaneously with OGTT blood samples.
- j 24 hour urine collection is done in subjects who give consent. 24 hour urine is collected from the morning of the previous day to the visit up to the morning of the visit. 24 hour urine collection is allowed to be done on a separate day of the study visit if collected within 7 days before the visit. Subjects do not need to perform 24 hour urine collection at visit 6 if they do not meet HbA1c ≥ 7% but ≤ 10% at Visit 5. At Visit 13(Week 12), 24 hour urine is not performed in subjects who did not complete Period C

Clinical Study Protocol
Drug Substance Dapagliflozin
Study Code D1692C00005
Edition Number 1
Date

k Includes anti-HAV (IgM, IgG), HBsAg, and anti-HCV, and anti-HBc

Table 2 Visit design and time windows

Visit ID	Visit description	Visit window
Visit 1	Enrolment (Screening) ^a	-12 weeks
Visit 2	Entry of washout ^b	-10 weeks ±3 days
Visit 3	Washout period ^b	-6 weeks ±3 days
Visit 4	Entry placebo lead-in	-4 weeks ±3 days
Visit 5	Placebo Lead-in Period	-1 week ±3 days
Visit 6	Randomisation/Start of treatment	±0 days
Visit 7	Treatment Period	1 week ±3 days after Visit 6
Visit 8	Treatment Period	2 weeks±3 days after Visit 6
Visit 9	Treatment Period	4 weeks ±3 days after Visit 6
Visit 10	Treatment Period	6 weeks ±3 days after Visit 6
Visit 11	Treatment Period	8 weeks ±3 days after Visit 6
Visit 12	Treatment Period	10 weeks ±3 days after Visit 6
Visit 13	Treatment Period/End of treatment	12 weeks ±3 days after Visit 6
Visit 14	Follow-up Period	16 weeks ±3 days after Visit 6

a If the results of central laboratory tests are available by Visit 2 (Week -10), Visit 1 can be done between 10 to 12 weeks before Visit 6.

b Strictly treatment naïve subjects at enrolment, Relatively treatment naïve subjects at enrolment, or subjects treated with anti-diabetic medication prior to enrolment can skip Visit 2 and Visit 3. If the results of central laboratory tests are available by Visit 4 (Week -4), Visit 1 can be done between 4 to 6 weeks before Visit 6.

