5.5.2 Doses and treatment regimens

Each dose will be composed of 3 tablets according to [Table 3](#) and [Table 4](#). Investigational drug should be taken once daily in the morning.

Period B:

Table 3 Composition of dose and number of tablets (Period B)

Dose	Investigational product
Placebo dose	1 mg placebo 1 tablet + 2.5 mg/5 mg placebo 1 tablet + 10 mg placebo 1 tablet

Period C:

Table 4 Composition of dose and number of tablets (Period C)

Dose	Investigational product
1 mg dose	1 mg 1 tablet + 2.5 mg/5 mg placebo 1 tablet + 10 mg placebo 1 tablet
2.5 mg dose	1 mg placebo 1 tablet + 2.5 mg 1 tablet + 10 mg placebo 1 tablet
5 mg dose	1 mg placebo 1 tablet + 5 mg 1 tablet + 10 mg placebo 1 tablet
10 mg dose	1 mg placebo 1 tablet + 2.5 mg/5 mg placebo 1 tablet + 10 mg 1 tablet
Placebo dose	1 mg placebo 1 tablet + 2.5 mg/5 mg placebo 1 tablet + 10 mg placebo 1 tablet

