6.3.1.2 Oral Glucose Tolerance Test (OGTT) Procedure

At Week 0, OGTT is performed in only those subjects whose FPG is less than 180 mg/dL at Week -1. At Week 12, OGTT is not performed in subjects who did not perform OGTT at Week 0, subjects who did not complete period C or subjects whose FPG \geq 180 mg/dL at Week 10.

- At Week 0 (randomization), study medication is given as soon as possible AFTER OGTT is complete
- At Week 12 (or at end of study visit), the study medication is given 1 hour BEFORE administration of 75 g oral glucose solution.
- Instruct subject to empty bladder after obtaining urine sample.
- Insert saline lock, if appropriate.

- Draw Time 0 blood sample for glucose, insulin, C-peptide
- Immediately after Time 0 blood sample is drawn above: Administer 75 g of oral glucose.
- Draw blood specimens for post prandial glucose, insulin and C-peptide at 60, 90, 120, 180 and 240 minutes.
- Collect all urine voided after emptying of bladder up to and including attempted void after removal of saline lock for the measurement of total volume urinary glucose, creatinine, and sodium concentration.
- Remove saline lock.

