6.5 Patient reported outcomes – Not Applicable

6.6 Pharmacokinetics

6.6.1 Collection of samples

Blood samples (3 mL) for determination of dapagliflozin in plasma will be taken at the times presented in the study plan (See [Table 1](#)). At visit 7, 10 and 12, plasma samples will be taken before administration of dapagliflozin. At visit 13, plasma samples will be taken at 60, 90, 120, 180 and 240 minutes after administration of dapagliflozin.

Samples will be collected, labelled stored and shipped as detailed in Laboratory Manual.

For blood volume see Section [7.1](#).

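### The Visit 13 morning dose is not governed by one clear rule, and the Week 12 OGTT and PK draws share a time grid counted from two different origins

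*Protocol*

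**What the plan says.** The dosing and sampling instructions for Visit 13 are spread over several places in the protocol.

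- **Default dosing (Section 5.5.2):** "Investigational drug should be taken once daily in the morning". No place of intake is given.
- **Visits with a withheld dose (Section 3.1, Period C):** "Subject should not take investigational products prior to study visit at Visit 7, 10 and 12 (Week 1, 6 and 10"). The next sentence reads "Investigational products should be taken soon after completing the study visit examinations" and names no visits.
- **PK at those three visits (Section 6.6.1):** "At visit 7, 10 and 12, plasma samples will be taken before administration of dapagliflozin".
- **Week 12 OGTT (Section 6.3.1.2):** "At Week 12 (or at end of study visit), the study medication is given 1 hour BEFORE administration of 75 g oral glucose solution". A Time 0 blood sample is drawn just before the glucose, and further draws are listed at 60, 90, 120, 180 and 240 minutes. Table 1 footnote h and Table 8 footnote d count the Visit 13 times from the glucose load.
- **Week 12 PK (Section 3.1, Visit 13):** "PK samples are obtained at 60, 90, 120, 180 and 240 minutes after administration of investigational products". Section 6.6.1 and Table 1 footnote i agree. Section 3.1 and the footnotes to Tables 1 and 8 add that, when an OGTT is done, PK and OGTT blood are taken at the same moments.
- **What the OGTT must deliver (Section 2.3):** glucose, insulin and C-peptide at 0, 30, 60, 120 and 180 minutes, and the AUC from 0 to 180 minutes.

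**The concern.** Section 3.1 reads as a complete list of visits at which the subject arrives undosed. A subject who follows it, together with the default of a morning dose, could take the Visit 13 dose at home. The site procedure in Section 6.3.1.2 cannot undo that. The Visit 13 dose timing appears only in the OGTT procedure, so it does not reach subjects who skip the OGTT because FPG was 180 mg/dL or more at Visit 5 or Visit 12. They still have PK samples timed from a dose.

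Visit 13 supplies the OGTT AUC, fasting insulin, fasting C-peptide and HOMA2 variables (tertiary) and FPG (secondary). It is also the only visit with post-dose PK samples for the exploratory exposure-response objective. Home dosing would lose or mistime OGTT and PK samples that cannot be retaken. It could also leave some Week 12 fasting samples pre-dose and others post-dose. A post-dose sample reflects active drug only in the dapagliflozin arms, so such a mixture could affect the contrast with placebo as well as add noise. The documents give no basis for sizing this.

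**Working it through.** The plan states no figure to reproduce here. The check sets the instructions side by side and does clock arithmetic on the stated times.

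**1. Does any instruction cover the home dose at Visit 13?**

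- Section 3.1 withholds the dose before Visits 7, 10 and 12. These are exactly the pre-dose PK visits of Section 6.6.1, which explains the list.
- Section 5.1 sets fasting and abstinence rules before visits but does not mention study drug.
- Section 6.3.1.2 fixes the dose relative to glucose, for subjects having an OGTT.
- No sentence directs a home dose on the Visit 13 day, and none forbids it. For subjects without an OGTT, no sentence ties the dose to the visit or to the fasting draw.
- If the sentence on dosing after the examinations applies to all of Period C, it clashes with Section 6.3.1.2, where the dose precedes the OGTT. If it applies only to the three listed visits, there is no clash. The text does not say which.

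**2. Can the two Week 12 grids coincide?**

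Dose to glucose is 60 minutes (Section 6.3.1.2), so minutes after glucose = minutes after dose − 60.

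| Reading of 60/90/120/180/240 | Minutes after dose | Minutes after glucose |
|---|---|---|
| Counted from the dose | 60/90/120/180/240 | 0/30/60/120/180 |
| Counted from the glucose | 120/150/180/240/300 | 60/90/120/180/240 |

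The first row reproduces the Section 2.3 grid exactly. The second contradicts the PK times and has no 30-minute draw. Draws cannot be simultaneous and also satisfy both rows.

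**3. Which reading do the blood volumes fit?**

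Table 8 allows 15 mL of PK blood at Visit 13. At 3 mL per sample (Section 6.6.1) that is 15 / 3 = 5 draws. It allows 10 mL for the OGTT, which is 10 / 5 = 2 mL for five draws, or 10 / 6 = 1.67 mL for Time 0 plus five. The per-draw OGTT volume is not stated. If it is 2 mL, the table fits five draws, as in the first row.

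**4. What would a home dose do?**

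Assume the dose is taken at home 2 or 3 hours before the glucose; the documents give no interval. Draws at 0 to 180 minutes after glucose then fall at 120 to 300 minutes (2 h) or 180 to 360 minutes (3 h) after the dose, instead of the intended 60 to 240. If the site instead keeps to times after the home dose, any sample due before the subject arrives is missed.

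**5. Would adding Visit 13 to the list be enough?**

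No. With the dose given at the visit, the two rows in step 2 still differ by 60 minutes. The sentence on dosing after the examinations would also then apply to Visit 13 and clash with Section 6.3.1.2.

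**The case against.** The strongest reply is that Visit 13 is left off the list for good reason. The listed visits are those with pre-dose PK, where the dose follows the examinations. Visit 13 has its own rule, with the dose given before the glucose. A dose given at the clinic on a fasting morning is that day's morning dose and complies with Sections 3.1, 5.5.2, 6.3.1.2 and 6.6.1, if the sentence on dosing after the examinations is confined to the listed visits. This stands. The omission is a gap in what subjects are told, not in itself a contradiction.

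A reader might infer that the rules cannot both be followed, or that subjects will take two doses on one morning. The documents support neither. A site that has subjects arrive undosed can comply, and a second dose would breach the once-daily instruction. Nor does a pre-dose baseline at Week 0 (Section 11.1) require Week 12 fasting samples to be pre-dose, since Week 0 precedes the first double-blind dose altogether.

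It is also fair to say that Section 11.4 uses actual sampling times for PK, that Section 5.7 has administration recorded in the CRF, and that the Laboratory Manual and eCRF are not shown. Actual times help the PK model only if the dose time is recorded too. The protocol expressly asks for the time of the last dose only for hypoglycaemic events (Section 6.4.9). Actual times cannot restore a missed draw.

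None of this answers the conflict between the two grids.

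**Conclusion.** The point holds in limited form, with two parts of different strength.

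- **The time grid is a true contradiction.** The same five times are counted from two events 60 minutes apart while the draws are called simultaneous. This rests on the protocol's own figures alone.
- **The Visit 13 dose is under-specified.** The protocol allows a compliant reading but does not secure it, least of all for subjects without an OGTT. Harm depends on how many subjects would dose at home, which the documents do not show. The shift to 120 to 300 or 180 to 360 minutes is an illustration under an assumed 2 or 3 hour interval.

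The exposed variables are the tertiary OGTT measures and exploratory PK, with a possible effect on Week 12 FPG and other fasting measures if pre- and post-dose samples are mixed. The primary HbA1c analysis and the sample size are unaffected.

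**What to change.** Reconcile Section 3.1 (the Period C and Visit 13 text and Table 1 footnotes h and i), Section 5.5.2, Section 6.3.1.2, Section 6.6.1 and the footnotes to Table 8 so that:

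1. one stated rule covers the morning dose on the Visit 13 day, for subjects with and without an OGTT, including its relation to the fasting sample;
2. the sentence on dosing after the examinations names the visits to which it applies;
3. one clock origin is named for the OGTT and PK draws, giving times consistent with the variables in Section 2.3.

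What the dosing rule should be is for the sponsor to decide. Record the clock time of the Visit 13 dose, and flag Week 12 samples that do not follow the reconciled rule.

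The cost is a short amendment with footnote edits, matching wording on the subject's card, and one time field in the eCRF if it is not already there.
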